#### 6.2.2.2 Neutropenia

Only neutropenia determined to be related to one or both study drugs require dose reductions or adjustments as described in this section. Colony-stimulating factor support (such as G-CSF or GM-CSF) for neutropenia is permissible at the discretion of the treating physician, but should not be given prophylactically. Participants who have treatment delayed for greater than four weeks should discontinue protocol therapy.

Dose modifications for neutropenia should be instituted as follows:

Grade	ANC	Modification
4	< 500	
First episode: Hold therapy until ANC resolves to grade <math>\leq 1</math> or baseline, then reduce carfilzomib by one dose level
 
Second episode: Hold therapy until ANC resolves to grade <math>\leq 1</math> or baseline, then further reduce carfilzomib by one more dose level and reduce PLD by one dose level
 
Third episode: Discontinue protocol therapy.

#### 6.2.2.3 F

#### **febrile Neutropenia (Fever > 38.5 degrees Celsius and ANC < 1000)**

Colony-stimulating factor support (such as G-CSF or GM-CSF) for neutropenia is permissible at the discretion of the treating physician, but should not be given prophylactically. Participants who have treatment delayed for greater than four weeks should discontinue protocol therapy.

Dose modifications for febrile neutropenia should be instituted as follows:

Grade	Modification
≥ 3	
First episode: Hold therapy until participant recovers, then reduce carfilzomib by one dose level
 
Second episode: Hold therapy until participant recovers, then further reduce carfilzomib by one more dose level and reduce PLD by one dose level
 
Third episode: Discontinue protocol therapy.

### 6.2.3 Dosing Modifications for Non-Hematologic Toxicities

Dose modification guidelines for treatment related non-hematologic toxicities are as follows:

Toxicity	Grade	Modification
Allergic reaction/hypersensitivity	2 or 3	
First episode: Hold suspected drug(s) until ≤ grade 1, resume treatment at full dose.
 
Second episode: Discontinue suspected drug(s).

Allergic reaction/hypersensitivity	4	Discontinue suspected drug(s).
Congestive heart failure (CHF)	Any	Any participant with new symptoms of CHF worsening symptoms of baseline CHF or LVEF < 45% should have all drugs held until resolution or return to baseline regardless of attribution, once resolved Carfilzomib may continue at the original dose, reduced dose or discontinued at the investigator's discretion, but PLD must be discontinued
Creatinine Clearance ≤ 15 mL/min (by Cockcroft-Gault formula, see Appendix C)	N/A	Hold all drugs until > 15mL/min regardless of attribution, then reduce suspected drug(s) by one dose level.
Herpes simplex virus (HSV) or herpes zoster	Any	Hold all drugs until HSV lesions are dry then resume treatment at full dose.

Infection	$\geq 3$	Hold all drugs until infection is adequately controlled with systemic therapy regardless of attribution, then resume treatment at full doses. Patients with recurrent infection should have carfilzomib or PLD dose reduced at the investigator's discretion.
Nausea, Vomiting, or Diarrhea persisting <math>\leq 3</math> days following adequate treatment of antiemetics or antidiarrheals	3	No dose modification required.
persisting <math>> 3</math> days following adequate treatment of antiemetics or antidiarrheals	3	Hold suspected study drug(s) until toxicity resolves to $\leq$ grade 1 or baseline, then reduce suspected drug(s) by one dose level.
Neuropathy Moderate symptoms; limiting instrumental ADL but not painful	2	Continue treatment. Patients on Pyridoxine should have it discontinued
Moderate symptoms with associated pain; limiting instrumental ADL	2	Continue treatment. Patients on Pyridoxine should have it discontinued. If neuropathy persists for more than two weeks, hold suspected drug(s) until resolved to $\leq$ grade 2 without pain, then reduce suspected drug(s) by one dose level.
Severe symptoms; limiting self care ADL	3	Continue treatment. Patients on Pyridoxine should have it discontinued. If neuropathy persists for more than two weeks, hold suspected drug(s) until resolved to $<$ grade 2 without pain, then reduce suspected drug(s) by one dose level.
Life-threatening consequences; urgent intervention indicated	4	Discontinue treatment.

Palmar-Plantar Erythrodyesthesia (PPE)  Erythema, desquamation, or swelling interfering with but not precluding normal physical activities; small blisters or ulcerations less than 2 cm in diameter
 
Blistering, ulceration, or swelling interfering with walking or normal daily activities; cannot wear regular clothing
 
Diffuse or local process causing infectious complications, a bed-ridden state or hospitalization
	
2
 
3
 
4
	
First episode: Hold all drugs until resolved to <math>\leq</math> grade 1 regardless of attribution, then resume at the same dose.
 
Second episode: Hold all drugs until resolved to <math>\leq</math> grade 1 regardless of attribution, then resume carfilzomib at same dose level a reduce PLD by one dose level.
 
Third episode: Hold all drugs until resolved to <math>\leq</math> grade 1 regardless of attribution, then resume carfilzomib at same dose and discontinue PLD
 
First episode: Hold all drugs until resolved to <math>\leq</math> grade 1 regardless of attribution, then resume carfilzomib at same dose level a reduce PLD by one dose level.
 
Second episode: Hold all drugs until resolved to <math>\leq</math> grade 1 regardless of attribution, then resume carfilzomib at same dose and discontinue PLD.
 
First episode: Hold all drugs until resolved to <math>\leq</math> grade 1 regardless of attribution, then resume carfilzomib at same dose and discontinue PLD.


Stomatitis  Painful erythema, edema, or ulcers, but can eat
 
Painful erythema, edema, or ulcers, and cannot eat
	
2
 
3
	
First episode: Hold all drugs until resolved to <math>\leq</math> grade 1 then resume at the same dose.
 
Second episode: Hold all drugs until resolved to <math>\leq</math> grade 1 then resume carfilzomib at the same dose and PLD at 20 mg/m^2.
 
Third episode: Hold all drugs until resolved to <math>\leq</math> grade 1 then discontinue PLD and resume carfilzomib at the same dose.
 
First episode: Hold all drugs until resolved to <math>\leq</math> grade 1 then resume carfilzomib at the same dose and PLD at 20 mg/m^2.
 
Second episode: Hold all drugs until resolved to <math>\leq</math> grade 1 then discontinue PLD and resume carfilzomib at the

Requires parenteral or enteral support	4	same dose. Hold all drugs until resolved to $\leq$ grade 1, then discontinue PLD and resume carfilzomib at the same dose.
Tumor lysis syndrome, defined as $\geq 3$ of following:  $\geq 50\%$ increase in creatinine $\geq 50\%$ increase in uric acid $\geq 50\%$ increase in phosphorus $\geq 30\%$ increase in potassium $\geq 20\%$ decrease in calcium $\geq 2$ -fold increase in LDH	Any	Hold all drugs until all abnormalities in serum chemistries have resolved to baseline, then resume treatment at full doses.
Other non-hematologic toxicity	$\geq 3$	Hold suspected study drug(s) until toxicity resolves to $<$ grade 1 or baseline, then reduce suspected drug(s) by one dose level.

### 6.3 Missed Doses

Missed doses will not be replaced during a cycle. Doses can be adjusted by +/- 2 days to allow for holidays, travel issues, etc. Additional adjustments may be granted at the PI's discretion. Everything possible should be done to prevent adjustments from in the study schedule during Cycle 1.

### 6.4 Changes in Body Surface Area (BSA)

Dose adjustments do not need to be made for weight gains/losses of  $\leq 20\%$  from baseline. Participants with a Body Surface Area (BSA) of greater than 2.2 m^2 will receive a capped dose using 2.2 m^2 as the cut-off value.

## 7.0 AGENT ADMINISTRATION

### 7.1 Carfilzomib

#### 7.1.1 Accountability

Instructions for the receipt, inspection, storage, preparation, administration, and disposal of Carfilzomib for Injection are provided in the Pharmacy Manual at each clinical site.

### 7.1.2 Availability

Carfilzomib for injection is supplied as a lyophilized parenteral product in single-use vials. Before use, the lyophilized product is reconstituted with water for injection to a final concentration of 2 mg/mL.

### 7.1.3 Storage, Stability, and Preparation

Lyophilized Carfilzomib for Injection is stored in a refrigerator at 2°C to 8°C. Carfilzomib doses are based on BSA. In a typical dose of carfilzomib, 27 mg/m^2 in a participant with a BSA of 2.0 m^2, the dose delivered would be 54 mg carfilzomib in a volume of 27 mL. Participants with a BSA of 2.2 m^2 or higher receive a dose based upon 2.2 m^2 BSA. After addition of the appropriate amount of Water for Injection and vigorous mixing, the solution is administered as an IV infusion.

### 7.1.4 Administration

The dosing schedule of carfilzomib will be on Days 1, 2, 8, 9, 15, and 16 in a 28-day cycle for 6 cycles and then weekly (Days 1, 8, 15, and 22) thereafter until disease progression or clinical relapse. Participants treated prior to approval of amendment 1, will have carfilzomib administered on Days 1, 2, 8, 9, 15, and 16 during Cycles 1 and 2 and on Days 1, 8, 15, and 22 beginning on Cycle 3. Carfilzomib dose levels being investigated are: 20mg/m^2, 20/27mg/m^2, 20/36mg/m^2, 20/45mg/m^2, and 20/56mg/m^2.

Current clinical experience indicates that carfilzomib can be safely administered as an IV push at rates of approximately 10 mL/minute for doses of 20-27mg/m^2. Higher doses (> 27 mg/m^2) should be administered as a 30-minute infusion. For IV infusion over 30 minutes, carfilzomib should be diluted into 50cc of 5% Dextrose Injection, USP (D5W). Based on preclinical studies, these adjustments in infusion rate and time should not affect the PDn effects in humans.

Each dose will consist of carfilzomib for injection administered on a mg/m^2 basis, and should be based on the participant's actual calculated body surface area (BSA) at baseline. Participants with a BSA > 2.2 m^2 will receive a dose based on a 2.2 m^2 BSA.

IV hydration will be given immediately before carfilzomib dose during Cycle 1. This will consist of 250 to 500 mL normal saline or other appropriate IV fluid. The goal of the hydration program is to maintain robust urine output (e.g., ≥ 2 L/day). Participants should be monitored periodically during this period for evidence of fluid overload.

Patients not receiving dexamethasone as part of the regimen (those treated in part

1 of phase 1) should receive 4mg dexamethasone premedication >30 minutes prior to all carfilzomib doses in cycle 1. Dexamethasone premedication can continue beyond cycle 1 at the discretion of the treating physician. Patients being treated with 10 or 20 mg dexamethasone as part of their regimen should not receive an additional 4mg as premedication.

Complete blood counts (CBC) with platelet count should be obtained and reviewed prior to carfilzomib dosing. See section 6.2.2 for guidelines for dose reductions, adjustments and delays for hematologic toxicities.

Appropriate chemistries, including creatinine should be obtained and reviewed prior to carfilzomib dosing during cycles 1 and 2. Electrolyte abnormalities that are National Cancer Institute (NCI) Common Terminology Criteria for Adverse Events (CTCAE) > 2 or clinically significant should be corrected prior to dosing. Renal function must be monitored closely during treatment with carfilzomib. Carfilzomib must be held for participants with a creatinine clearance (by Cockcroft-Gault formula see Appendix C) < 15 mL/min at any time during study participation.

Participants with laboratory abnormalities consistent with TLS should not receive the scheduled dose. Lab abnormalities consistent with TLS is defined as  $\geq 3$  of following: serum creatinine  $\geq 50\%$  increase, uric acid  $\geq 50\%$  increase, phosphorus  $\geq 50\%$  increase, potassium  $\geq 30\%$  increase, calcium  $\geq 20\%$  decrease, LDH  $\geq 2$ -fold increase prior to dosing should not receive the scheduled dose. Participants with such abnormalities should be re-evaluated again within the next 24 hours (or sooner, if clinically indicated) and then periodically as clinically indicated.

Participants should have a dedicated line for carfilzomib administration. Before and after administration, the line must be flushed with a minimum of 20 mL of normal saline. If a dedicated line is not possible, the existing line must be flushed with a minimum of 20 mL of normal saline before and after drug administration.

Participants may experience stinging, burning, or a painful sensation at the injection site during the IV push administration of carfilzomib. This generally is mild and subsides shortly following the infusion. Slowing the IV push to the maximum allowed time (10 minutes) can help with minimize such a reaction.

Carfilzomib is considered an irritant. Nonetheless, care should be taken to avoid extravasation. If any signs or symptoms of extravasation occur, the infusion should be terminated and restarted in another vein. Apply ice immediately for 30-60 minutes, subsequently alternating on and off every 15 minutes for 24 hours. The extremity should be monitored for 24-48 hours, then the participant may resume normal activity as tolerated. Do not apply heat or sodium bicarbonate. If pain, erythema or swelling persists beyond 48 hours the participant should be referred to a plastic surgeon for possible debridement at the treating physician's discretion.

The dose will be administered at a facility capable of managing hypersensitivity reactions. Medications to treat infusion-related reactions, as well as emergency equipment should be available for immediate use. If a patient develops a grade  $\geq 2$  infusion-related reaction, the infusion should be stopped and appropriate symptomatic treatment per institutional guidelines should be started immediately. The participant should be observed for at least 30 to 60 minutes depending on the severity of the reaction. At the discretion of the treating physician, treatment may be resumed. Discontinue treatment if subsequent infusion-related reaction occurs.

In the event of  $\geq$  grade 2 infusion-related or hypersensitivity reaction during carfilzomib infusion, discontinue the carfilzomib injection. Begin appropriate symptomatic treatment immediately per institutional guidelines. The participant should be observed for at least 30 to 60 minutes depending on the severity of the reaction. At the discretion of the treating physician, treatment may be resumed. Discontinue treatment if subsequent infusion-related reaction occurs.

Procedures for dose reductions, adjustments and delays are summarized in Section 6.0.

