## **6.2 Dosing Modifications**

### **6.2.1 Overview**

Dose modifications for hematologic and non-hematologic toxicities are summarized in sections 6.2.2 and 6.2.3 respectively. Participants who have treatment delayed for greater than four weeks should discontinue protocol therapy.

A maximum of 2 dose reductions of carfilzomib or Dex and 1 dose reduction of PLD will be allowed for each participant. More than two dose reductions of Dex or one dose reduction of PLD will require the agent be discontinued. Participants that permanently discontinue Dex or PLD due to toxicity can remain on study and receive the other planned study drug doses at the investigator's discretion. Participants requiring a third dose reduction of carfilzomib will have treatment discontinued.

If the participant tolerates the reduced dose for one cycle, the participant may be dose escalated to the study drug dose(s) prior to reduction at the discretion of the Investigator.

Dose modifications should be followed directly for Cycle 1 for all patients treated in the phase I portion of the study. In Cycles 2+ for patients treated in the phase I portion, and for any cycle for patients treated in the phase II portion, dose modifications and delays different from those stated in the protocol for management of toxicities will be permitted at the discretion of the Principal Investigator.

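### Section 7.1.4 lets the treating physician restart carfilzomib after a hypersensitivity reaction of any grade from 2 up, whereas Section 6.2.3 says to discontinue the suspected drug at grade 4

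*Combined protocol and SAP*

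**What the plan says.** Section 6.2.3 grades allergic and hypersensitivity reactions. After a first grade 2 or 3 episode the suspected drug is held until the reaction is at or below "grade 1, resume treatment at full dose"; a second episode ends that drug. At grade 4 there is no hold-and-resume step (the entry reads "Discontinue suspected drug(s").

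Section 7.1.4 has two reaction paragraphs for carfilzomib. The first concerns infusion-related reactions of grade 2 or higher. The second adds hypersensitivity, its trigger being a greater-or-equal sign followed by "grade 2 infusion-related or hypersensitivity reaction during carfilzomib infusion, discontinue the carfilzomib injection". It then sets a minimum watch: "The participant should be observed for at least 30 to 60 minutes depending on the severity of the reaction". It closes: "At the discretion of the treating physician, treatment may be resumed. Discontinue treatment if subsequent infusion-related reaction occurs". Section 7.2.5 has a similar rule for PLD, which names infusion-related reactions only and adds H1-blockers and/or steroids on restarting.

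On the standing of the modification rules, Section 6.2.1 says: "Dose modifications should be followed directly for Cycle 1 for all patients treated in the phase I portion of the study". For later phase I cycles and every phase II cycle, different modifications and delays "will be permitted at the discretion of the Principal Investigator".

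**The concern.** Section 7.1.4 is the text in use while a participant is reacting. It reads as a complete sequence: stop, treat, observe, and restart if the physician judges it right. Nothing in it sends a grade 4 hypersensitivity reaction down a different path. A physician following it as written has permission to re-expose a participant to the suspected drug after a reaction for which the grade-specific table offers only discontinuation. What is at stake is participant safety and consistent handling of a life-threatening event.

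**Working it through.** The point rests on no sample size, error rate or event figure, so the check sets the texts side by side.

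| Hypersensitivity reaction during carfilzomib | Section 6.2.3 | Section 7.1.4, second reaction paragraph | Result |
|---|---|---|---|
| First, grade 2 or 3 | Hold; full dose once at grade 1 or lower | Physician may restart after treatment and observation | Both allow a restart; 7.1.4 is silent on recovery to grade 1 |
| First, grade 4 | Discontinue suspected drug | Physician may restart; no upper grade limit | Conflict |

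1. *Could the instruction in 7.1.4 to discontinue the injection mean a permanent stop?* No. The same paragraph goes on to allow a restart, so it refers to the administration in progress.

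2. *How many sentences are affected?* Section 7 has 3 restart sentences: 2 in 7.1.4 and 1 in 7.2.5. None of the 3 has a grade 4 exception, and none requires recovery to grade 1 or lower. Only 1 of the 3, in the second paragraph of 7.1.4, names hypersensitivity. The direct conflict is therefore in one sentence.

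3. *PLD.* The trigger in 7.2.5 does not mention hypersensitivity. The section does report anaphylactic and anaphylactoid events among infusion reactions, some life-threatening or fatal. The overlap with the grade 4 row is possible, but only for a reaction that is allergic or anaphylactic in kind.

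4. *Does the pointer to Section 6.0 settle it?* It closes both 7.1.4 and 7.2.5, but it covers reducing, adjusting and delaying doses. It does not mention discontinuation or say which section prevails.

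5. *Does 6.2.1 settle it?* In phase I Cycle 1 it favours 6.2.3. Elsewhere it lets the Principal Investigator permit departures, whereas 7.1.4 gives the restart decision to the treating physician. It does not authorise what 7.1.4 allows, and it does not say that 6.2.3 limits 7.1.4.

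6. *Do the other safeguards settle it?* The relevant removal criterion in 8.1 depends on the Investigator's judgment. Reporting to the Principal Investigator within 24 hours (13.10) can come after a restart decision, because the minimum observation is 30 to 60 minutes.

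**The case against.** The best case against the point is that the sections can be read together. Section 7.1.4 is general chair-side management, and its permission is discretionary. Section 6.2.3 is the specific, graded table, and a general permission need not displace a specific instruction. The pointer to Section 6.0 leads to tables whose modification column includes discontinuation, so a careful reader would reach the grade 4 row. Section 6.2.3 also introduces its entries as guidelines, and 6.2.1 allows departures outside phase I Cycle 1. There, the remaining difference is who decides, not whether a restart is ever possible.

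Much of this stands. It rules out the reading that 6.2.3 is an absolute bar throughout the trial. It also rules out the reading that all three restart sentences contradict 6.2.3, since two of them do not name hypersensitivity. The missing recovery condition for grade 2 or 3 is an omission in Section 7 and not a contradiction.

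The grade 4 permission itself survives. The reconciliation has to be inferred by someone managing an acute reaction, and no sentence states it.

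**Conclusion.** The conflict is real and narrow. After a first grade 4 hypersensitivity reaction to carfilzomib, 6.2.3 says to discontinue while 7.1.4 leaves a restart to the treating physician, and nothing in the document says which prevails. For PLD it holds only by overlap.

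A reader might infer that physicians are forced to breach one rule or the other. They are not, because a physician who discontinues breaches neither. A reader might also infer harm to the trial's results. No effect on the primary endpoint, DLT classification or phase II decision rule is shown. The documents give no rate of grade 4 hypersensitivity for either drug, and none is assumed here, so the size of the problem is one conflicting sentence and not an expected number of events. The conclusion assumes only that the trigger in 7.1.4 means what it says, with no upper limit on grade. It merits correction because it concerns re-exposure after a life-threatening reaction and is easily put right.

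**What to change.** In the second reaction paragraph of 7.1.4, replace the restart sentence with: *After a first grade 2 or 3 reaction the treating physician may restart treatment; if the reaction was hypersensitivity, only once it has settled to grade 1 or lower. After a grade 4 allergic or hypersensitivity reaction, including anaphylaxis, discontinue the suspected drug(s). Section 6.2.3 governs allergic and hypersensitivity reactions.*

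Add a one-line cross-reference to 6.2.3 for allergic or anaphylactic reactions in the first reaction paragraph of 7.1.4 and in 7.2.5. In 6.2.1, state that the Principal Investigator's discretion does not extend to rechallenge after a grade 4 hypersensitivity reaction; otherwise the new wording would conflict with that discretion.

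Keep the stop on any further infusion-related reaction and the H1-blocker and steroid provision for PLD. Non-allergic infusion-related reactions of grade 3 or higher stay under "Other non-hematologic toxicity" in 6.2.3.

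The cost is one reworded sentence and three short additions in a protocol amendment. It adds no visits, procedures or participants and removes no existing safeguard. It does withdraw the Principal Investigator's latitude for this one kind of event.

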### **7.1.5 Guidelines for Monitoring and Treatment of Tumor Lysis Syndrome**

Tumor Lysis Syndrome (TLS), which may be associated with multiorgan failure, has been observed in treatment Cycles 1 and 2 in some participants with MM who have been treated with carfilzomib.

